2.7.2. Laboratory Evaluations

Individual clinical lab (hematology, serum chemistry, and coagulation parameters) values will be listed by visit and summarized using descriptive statistics as appropriate (sample size, mean, standard deviation, median, minimum and maximum) for continuous data and frequency counts for categorical data. Individual changes from baseline (Visit 1) in laboratory values will be calculated and summarized descriptively for continuous variables. Shift tables from baseline (Visit 1) to post dose (Visit 4 and Visit 7) will also be produced for the laboratory assessments based on the categories of Low, Normal, and High.

A clinically significant abnormal value or clinically significant change from baseline (Visit 1), may be recorded as an AE, if deemed appropriate by the PI or sponsor.

2.7.3. Vital Signs

Individual vital sign measurements (height, weight, seated SBP/DBP and heart rate) will be listed by measurement time and summarized using descriptive statistics as appropriate (sample size, mean, standard deviation, median, minimum and maximum). Individual changes from baseline (pre-dose Visit 1) in vital sign measurements will be calculated and summarized descriptively.

A clinically significant change from baseline may be recorded as an AE, if deemed appropriate by the PI or sponsor.

2.7.4. Physical Examination

Individual physical examination findings will be listed by visit.

A clinically significant change from start of randomized treatment will be recorded as an AE if deemed appropriate by the Investigator.

2.8. PK/PD Evaluations

Trough PK concentrations will be summarized using descriptive statistics (sample size, mean, standard deviation, median, minimum and maximum) at each visit in which PK is collected.

2.9. Efficacy Evaluations

2.9.1. Primary Efficacy Evaluation

There are two primary endpoints for this study: Percent change in PASI and sIGA response rate.

Percent change in PASI will be analyzed using a linear mixed model analysis. The model will be implemented using PROC MIXED in SAS, and will include fixed effects for treatment, site and Baseline PASI as a covariate.

The sIGA response rate will be analyzed using Fisher's Exact Test with treatment and response as the factors.

2.9.2. Secondary and Exploratory Efficacy Evaluations

Continuous variables will be analyzed using a linear mixed model similar to the primary efficacy evaluation.

Response rates and other dichotomous variables will be analyzed using Fisher's Exact Test.

Categorical data that has more than two possible responses will be analyzed using the Cochran-Mantel-Haenszel Row Mean Score.

2.9.3. Psoriasis Area and Severity Index (PASI)

PASI total score, change from baseline and percent change from baseline will be calculated for each post-baseline visit. The difference between active and placebo will be tested using a mixed effects linear model (PROC MIXED in SAS) that will include fixed effects for treatment and site with Baseline PASI total score as a covariate at each post-baseline visit.

PASI75 (75% improvement from baseline in PASI total score) and PASI50 (50% improvement from baseline in PASI total score) responder rates will be derived and analyzed using a Fisher's exact test to test for differences between placebo and active at Weeks 1, 3, 7, 11 and 15.

2.9.4. static Investigator Global Assessment (sIGA)

The sIGA will be summarized at each visit using frequency counts. The difference between active and placebo will be tested using a Cochran-Mantel-Haenszel (CMH) test at each visit that sIGA is collected.

Treatment success in sIGA is defined as having a value of clear=0 or almost clear=1 and greater than or equal to a 2 point improvement on the 5-point static Investigator's Global Assessment test. Responder rates based on treatment success will be summarized and analyzed using a Fisher's Exact test at each post-baseline visit that sIGA is collected.

2.9.5. Psoriasis Body Surface Area (BSA) Involvement

Observed, change from baseline and percent change from baseline in BSA will be derived and analyzed using a mixed effects linear model (PROC MIXED in SAS) that will include fixed effects for treatment and site with Baseline BSA as a covariate at each post-baseline visit.

2.9.6. Dermatology Life Quality Index (DLQI)

The DLQI total score will be derived at each visit in which DLQI is collected. The observed, change from baseline and percent change from baseline in DLQI total score will be derived and analyzed using a mixed effects linear model (PROC MIXED in SAS) that will include fixed effects for treatment and site with Baseline DLQI total score as a covariate at each post-baseline visit.

Each question on the DLQI is scored on a four-point Likert scale:

- Very much = 3
- A lot = 2
- A little = 1
- Not at all = 0
- Not relevant = 0
- Question unanswered = 0

The DLQI total score is calculated by adding the score of each question, resulting in a maximum of 30 and a minimum of 0. The higher the score, the more quality of life is impaired. A score higher than 10 indicates that the patient's life is being severely affected by their skin disease.

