The IGA is a 5-category scale including “0 = clear”, “1 = almost clear”, “2 = mild”, “3 = moderate” or “4 = severe” indicating the physician’s overall assessment of the psoriasis severity focusing on induration, erythema and scaling. Treatment success of “clear” or “almost clear” consists of no signs of psoriasis or normal to pink coloration of lesions, no thickening of the plaque, and none to minimal focal scaling. The IGA captures and categorizes the global assessment of all clinical signs and symptoms of disease. This scale will be scored as a static assessment; i.e., without regard to a previous assessment. To have IGA success, one must have a designation of ‘clear’ or ‘almost clear’ and exhibit a two-point improvement from Baseline. Hence, if a subject has ‘mild’ disease at Baseline, he/she must reach ‘clear’. If a subject has ‘moderate’ disease at Baseline, he/she must reach ‘almost clear’.

And, if a subject is classified as ‘severe’ at Baseline, he/she must still reach ‘almost clear’, even though that requires a three-point improvement.

Training will be mandatory for trial investigators involved in this assessment.

- **Itch Numeric Rating Scale (I-NRS)**

The Itch NRS is a self-administered subject reported outcome questionnaire that is completed during protocol specified clinic visits. Participants indicate itch severity by circling the integer that best describes the worst level of itching due to psoriasis in the past 24 h on an 11-point scale anchored at 0, representing ‘no itching’ and 10, representing ‘worst itch imaginable’.

- **Dermatology Life Quality Index (DLQI)**

DLQI is the dermatology-specific quality of life measure used for psoriatic population. The 10-item questionnaire assesses participant health-related quality of life (daily activities, personal relationships, symptoms and feelings, leisure, work and school, and treatment). The DLQI questions are rated by the participant as 0 (not at all/not relevant) to 3 (very much) with a total score range of 0 (best) to 30 (worst); higher scores indicate poor quality of life. Patient's Global

Assessment (PtGA)-The PtGA asks the participant to evaluate the overall cutaneous disease at that point in time on a single item, 5-point scale (0=clear; 1=almost clear; 2=mild; 3=moderate; 4=severe).

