2.13. Handling Missing Data

Descriptive statistics and listings will be provided for all data. No substitution of missing data will be used in any calculations. Data points that appear to be spurious will be investigated and will not be excluded from the listings. Influential cases will be handled in an appropriate statistical manner.

Dates related to the adverse events and medications will be imputed using the rules below in an effort to categorize them properly into the summary tables.

Imputing partial or missing start dates:

- If the year is unknown, then the start date will not be imputed. The date will remain missing.
- If the month is unknown and the year is the same as the first dose date of the study, then impute the month and day of the date to be equal to the first dose month and day. Otherwise, impute the month as January.
- If the day is unknown and the month and year are the same as the first dose date of the study, then impute the day to be equal to the day of the first dose. Otherwise, impute the day as '01'.

Impute partial or missing stop dates:

- If the year is unknown, then the stop date will not be imputed. The date will remain missing.
- If the month is unknown, impute the month as December.
- If the day is unknown, impute the day to be the last day of the month.

If an imputed stop date is greater than the date of study completion/discontinuation date of the study, then the imputed stop date will be set equal to the date of completion/discontinuation date.

The imputed dates will be stored in the analysis datasets along with the original dates as recorded by the sites.

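### The SAP scores every unanswered DLQI item 0, the most favourable value, with no limit on blanks and in conflict with its own no-substitution rule

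*SAP*

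**What the plan says.** The DLQI has ten items, each scored 0 to 3. SAP 2.9.6 sums them: "The DLQI total score is calculated by adding the score of each question, resulting in a maximum of 30 and a minimum of 0". It gives the direction as "The higher the score, the more quality of life is impaired", and protocol 3.1 agrees: "with a total score range of 0 (best) to 30 (worst); higher scores indicate poor quality of life".

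In its list of item scores, SAP 2.9.6 includes "Question unanswered = 0", the same value as for *not at all* and *not relevant*. It does not limit how many items may be blank, and it never says when a total is missing. Protocol 3.1 gives 0 only to *not at all* and *not relevant* and has no rule for an unanswered item.

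SAP 2.13 says "No substitution of missing data will be used in any calculations", and protocol 8.7.7 has the same sentence. Neither document mentions the DLQI rule as an exception.

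Change from Baseline in DLQI at Weeks 3, 7, 11 and 15 is one of the six secondary efficacy endpoints in SAP 1.3.5. SAP 2.9.6 models the observed total, the change and the percent change, with the Baseline total as covariate.

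**The concern.** A blank item carries no information about quality of life, yet the rule gives it the value for no impairment. Without a cap, the fewer items a subject answers, the better the recorded total can look.

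The zeros enter the analysis in three places: the outcome at each post-baseline visit, the Baseline covariate, and the denominator of percent change. A Baseline total of 0 from a blank form would leave percent change undefined.

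The two SAP sections also give different instructions. A programmer following 2.9.6 and one following 2.13 would derive different totals from the same incomplete form, so the conflict needs settling however large the bias proves to be.

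**Working it through.** **Inputs from the documents.** Ten items (protocol 3.1); item scores 0 to 3, unanswered = 0, total = sum of items, and a total above 10 as the SAP's mark of severe impact (all SAP 2.9.6). Neither document gives a rate of unanswered items or a DLQI mean, so those are assumed below.

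**1. Stated range.** 10 × 0 = 0 and 10 × 3 = 30. This reproduces the SAP's minimum and maximum.

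**2. Effect on one form.** With m blanks, the total falls by the sum of the scores those items would have had. That is 0 to 3m points: at most 3 for one blank, 6 for two and 9 for three. It is 0 if the true answers were *not at all* or *not relevant*.

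For illustration, assume equal item scores, so that the recorded total is T × (10 − m)/10. With an assumed true total T = 12:

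| Blanks m | Recorded total | Shift | Shift as % of T |
|---|---|---|---|
| 1 | 10.8 | −1.2 | −10% |
| 2 | 9.6 | −2.4 | −20% |
| 5 | 6.0 | −6.0 | −50% |
| 10 | 0 | −12.0 | −100% |

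Two blanks take this subject from above 10 to below it. With T = 11, one blank is enough: 11 × 9/10 = 9.9.

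**3. Direction depends on the visit.** Take a subject whose true total is 12 at both Baseline and Week 15, so the true change is 0.

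- Two blanks at Week 15: 9.6 − 12 = −2.4, or −2.4/12 = −20%, a false improvement.
- Two blanks at Baseline: 12 − 9.6 = +2.4, or 2.4/9.6 = +25%, a false worsening.

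**4. Effect on the between-arm difference at a post-baseline visit.** Let d be the difference between arms in the share of forms with m blanks, and s the mean score the blank items would have had, taken as equal in both arms. Then the bias is d × m × s, in favour of the arm with more blanks. Assume d = 0.05 to 0.20 and s = 1 to 2:

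| Blanks per affected form | Lowest | Highest |
|---|---|---|
| 1 | 0.05 × 1 × 1 = 0.05 | 0.20 × 1 × 2 = 0.4 |
| 2 | 0.05 × 2 × 1 = 0.1 | 0.20 × 2 × 2 = 0.8 |
| 10 (wholly blank, scored 0) | 0.05 × 10 × 1 = 0.5 | 0.20 × 10 × 2 = 4.0 |

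If d = 0, the bias is 0.

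**5. With a cap at two blanks.** Only the one-blank row remains. The largest possible error on a form that stays in the analysis falls from 30 points (10 × 3) to 3 if the existing 0 is kept for a single blank. Prorating instead would give 9.9 × 10/9 = 11.0 in the T = 11 example, though that exact recovery depends on equal item scores.

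**The case against.** The best defence is that 2.9.6 is a specific, prespecified scoring rule and 2.13 a general one. Section 2.13 itself goes on to impute partial dates, so it is not absolute. Protocol section 8 leaves further detail to the SAP, so filling a gap in the protocol is not a fault. All of this is fair, but it settles only which sentence takes precedence. It does not supply a cap or make 0 a sound value for a heavily incomplete form.

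The DLQI is completed at clinic visits, and protocol 9.1.1 has omissions queried. Forms with many blanks should therefore be rare, and a few scattered single blanks would matter little. This makes blanks less frequent but leaves their scoring unchanged.

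A form with no answers could also be read as not collected, and so missing under 2.13. The SAP does not say this, and the literal rule gives 0. The 0.5 to 4.0 point range applies only on the literal reading.

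A reader might infer that the rule turns missing answers into improvement generally, or that it favours orticumab. The documents support neither. Baseline blanks work the other way, blanks that stand for *not at all* or *not relevant* change nothing, and nothing in the documents suggests more blanks in one arm. Whether the rule follows the instrument's own scoring instructions cannot be checked from these documents, and the point does not rest on it.

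Finally, prorating a single blank is itself substitution, so it has no claim over the existing 0 on grounds of consistency. That choice is the sponsor's.

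**Conclusion.** The concern holds as a fault in a stated rule for a secondary endpoint. Blank items receive the most favourable score without limit, and the rule contradicts the no-substitution sentence in both documents. Each blank costs 0 to 3 points at its visit, with opposite effects on change from Baseline depending on whether it falls before or after treatment starts.

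Between-arm bias requires unequal blanks. Under the assumed 5 to 20 percentage point difference and mean item score of 1 to 2, it is 0.05 to 0.4 points for one blank per affected form, and 0.5 to 4.0 points only if wholly blank forms are scored 0. These are illustrations, because the documents give neither blank rates nor a DLQI standard deviation against which to judge them. The PASI and sIGA primary analyses are not touched.

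**What to change.** - In SAP 2.9.6, set the DLQI total to missing for a visit when two or more items are unanswered. This covers the wholly blank form.
- Keep one prespecified rule for a single blank, either the existing 0 or prorating from the nine answered items, and apply it at Baseline and at every later visit.
- In SAP 2.13, name that rule as an exception to the no-substitution statement.
- Report the number of unanswered items by arm and visit, so that readers can see whether the rule mattered.

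The cost is a few sentences in the SAP, a small change to the derivation and one short summary. A few incomplete forms drop out of a secondary analysis. If blanks are related to quality of life, dropping those forms carries some bias of its own, which is a further reason to report them by arm. The cut-off of two is a judgement and does not come from the documents. The essential parts are that a cap exists and that 2.9.6 and 2.13 agree.

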2.9.7. Coronary Computed Tomographic Angiography (CCTA)

The observed and change in coronary artery perivascular fat attenuation index (FAI) measured by coronary computed tomographic angiography (CCTA) will be summarized and analyzed using a mixed effects linear model (PROC MIXED in SAS) that will include fixed effects for treatment and site with Baseline FAI as a covariate at each post-baseline visit in which CCTA is performed.

The observed and change in noncalcified and low attenuation coronary artery plaque volume, assessed by CCTA will be summarized and analyzed using a mixed effects linear model (PROC MIXED in SAS) that will include fixed effects for treatment and site with baseline value as a covariate at each post-baseline visit in which CCTA is performed.

The observed and change in total plaque volume, assessed by CCTA will be summarized and analyzed using a mixed effects linear model (PROC MIXED in SAS) that will include fixed effects for treatment and site with Baseline Total Plaque Volume as a covariate at each post-baseline visit in which CCTA is performed.

2.9.8. Itch Numeric Rating Scale (I-NRS)

The I-NRS will be summarized at each visit using frequency counts. The difference between active and placebo will be tested using a Cochran-Mantel-Haenszel (CMH) test at each visit that I-NRS is collected.

2.9.9. Cardiometabolic and Inflammatory Biomarkers

The biomarkers will be analyzed according to standard ELISA multiplexes which provide quantitative values. There may be LLOQ for some subjects for some biomarkers, but the ones chosen are the more common and suspected to be elevated in these subjects.

The observed value and change from baseline in the biomarkers will be summarized (number of observations with BLQ values, n, mean, std. dev., median, minimum and maximum) and analyzed using a mixed effects linear model (PROC MIXED in SAS) that will include fixed effects for treatment and site with baseline value as a covariate at each post-baseline visit in which biomarkers are collected.

2.10. Interim Analyses

This study will utilize a modified adaptive design model. There will be 2 planned stages for the analysis. Stage 1 will consist of the first 30 randomized subjects. After enrollment is completed for Stage 1, enrollment will begin for Stage 2 (there will be no pause in enrollment).

In order to ensure an overall alpha of approximately 0.05, Stage 1 will be analyzed at an alpha level of 0.01 and the final analysis (Stage 1 and Stage 2 combined) will be analyzed at an alpha level of 0.04. A hierarchical testing strategy will be utilized in which the percentage change in PASI will be tested initially. If the p-value for this initial test is less than the indicated alpha level, the result will be concluded as real. If the percentage change in PASI is concluded as real, the change in sIGA will be tested at the indicated alpha level.

In order to preserve type I error, the method presented by Cui, et al will be used to combine the data from Stage 1 and Stage 2.

The planned number of subjects for the study is 75. Stage 1 will consist of the first 30 subjects, so the weight given to Stage 1 in the analyses will be 30/75 (0.40). The weight given to Stage 2 in the analyses will be 45/75 (0.60).

The combining of the Stage 1 and Stage 2 analyses will be performed as follows:

- The Stage 1 p-value will be converted to a Z score (standard normal score).
- The Stage 2 p-value will be converted to a Z score (standard normal score).
- The Z scores will be combined using the weights previously indicated to create the combined Z score.
- The combined Z score will be converted to a p-value.

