2.15. Computer Systems and Packages Used for Statistical Analyses

Server SAS® version 9.4 on the Microsoft Windows Server 2008R2 64-bit platform will be used for all analyses. All computations will be performed using SAS®. The exact form of the various algorithms will be the SAS® defaults. The output from any SAS® procedure will be used in the tables using SAS® macros.

3. References

Cui, L, HM Hung, and SJ Wang, 1999, Modification of Sample Size in Group Sequential Clinical Trials, Biometrics, 55(3):853–857.

4. Data Listing Shells

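### The final test combines the stage Z scores with unscaled weights 0.40 and 0.60, so as written the two looks use about 0.014 of the 0.05 and power for PASI falls to about 54%

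*SAP*

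**What the plan says.** SAP 2.10 and protocol 8.8 describe the same two-stage plan. Stage 1 is the first 30 randomized subjects of a planned 75. The overall target and the level for the first look are given together: "In order to ensure an overall alpha of approximately 0.05, Stage 1 will be analyzed at an alpha level of 0.01". For the second look, the plan states that "the final analysis (Stage 1 and Stage 2 combined) will be analyzed at an alpha level of 0.04".

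On the weights, "the weight given to Stage 1 in the analyses will be 30/75 (0.40") and "The weight given to Stage 2 in the analyses will be 45/75 (0.60"). Each stage p-value is turned into a standard normal score, and then "The Z scores will be combined using the weights previously indicated to create the combined Z score". The combined score is converted back to a p-value. No square root or rescaling appears in the steps.

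Both documents also state that "the method presented by Cui, et al will be used to combine the data from Stage 1 and Stage 2", but neither reproduces that method's formula. Neither says whether the tests are one- or two-sided, or how the direction of effect is kept when a p-value becomes a Z score. SAP 2.15 says only that "The exact form of the various algorithms will be the SAS® defaults".

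**The concern.** A weighted sum of two independent standard normal scores is itself standard normal only if the squared weights add to 1. Here the weights themselves add to 1, so the squared weights do not. The combined score is too narrow, and comparing it with standard normal limits makes the final test much stricter than its label.

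At stake is the main analysis of a small trial. PASI is tested first and sIGA only if PASI succeeds, so power lost on PASI also lowers the chance of reaching sIGA at all. The missing sign rule matters in the other direction: a two-sided p-value carries no sign, and combining unsigned scores lets opposite effects in the two stages reinforce each other.

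**Working it through.** **Inputs.** Levels 0.01 and 0.04, and weights 0.40 and 0.60 (SAP 2.10). SD 10 and differences of 7 and 8 points (SAP 2.11). Allocation 2:1. N = 75 planned or 60 completers (protocol 4.1). Two-sided testing is assumed, with one-sided results given as the range.

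**1. The plan's own figures.** 0.01 + 0.04 = 0.05, the additive bound. A single look at 0.05 with N = 75 gives 81.5% power for 7 points and 90.4% for 8, which matches the SAP's 80% and 90%. Those power figures therefore do not reflect the two-look procedure.

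**2. The final test as written.**
- Variance of 0.4\*Z1 + 0.6\*Z2 = 0.16 + 0.36 = 0.52; SD = 0.721.
- Limit for a nominal 0.04 = 2.054. In true SD units, 2.054 / 0.721 = 2.848, so the true level is 0.0044 (one-sided 0.0076).
- Either look, by bivariate normal with correlation 0.4 / 0.721 = 0.555: overall error 0.0137 (one-sided 0.0163).

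**3. The final test with square-root weights.** sqrt(0.4)\*Z1 + sqrt(0.6)\*Z2 has variance 1 and correlation sqrt(0.4) = 0.632 with Stage 1. Overall error is 0.0461 (one-sided 0.0453).

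**4. Power for PASI, N = 75, 7 points.**
- SE = 10\*sqrt(1/50 + 1/25) = 2.449; standardized effect = 7 / 2.449 = 2.858.
- Stage means: 2.858\*sqrt(0.4) = 1.807 and 2.858\*sqrt(0.6) = 2.214.
- As written, the combined mean is 0.4\*1.807 + 0.6\*2.214 = 2.051, almost exactly on the 2.054 limit. The final look alone therefore has about 50% power.
- With square-root weights the combined mean is 2.858.

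Two-look power (rejection at either look):

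| N | Difference | Weights as written | Square-root weights |
|---|---|---|---|
| 75 | 7 | 54% | 79.4% |
| 75 | 8 | 69% | 89.0% |
| 60 | 7 | 43% | 69.9% |
| 60 | 8 | 57% | 81.2% |

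**5. Sign of the stage scores.** If two-sided p-values are converted to unsigned |Z| and combined with square-root weights, overall error is about 0.080 (4 million simulated trials). With signed scores the same simulation gives 0.046.

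**6. Optional final level.** With square-root weights, two-sided, and Stage 1 kept at 0.01, a final level of 0.0440 gives overall error 0.0499; 0.0441 gives 0.05003, just over. Two-look power for 7 points rises from 79.4% to 80.5% at N = 75 and from 69.9% to 71.2% at N = 60. Without rescaling the weights, moving to 0.0441 only takes overall error from 0.0137 to 0.0144 and power at N = 75 from about 54% to 56%.

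**The case against.** **The cited method may already settle the scaling.** A statistician who programs from the citation rather than from the listed steps may well scale the weights, and then the large loss does not occur. This stands as far as it goes. But the documents do not give the formula, and the steps name the weights explicitly. At best the text is ambiguous between a procedure with overall error 0.046 and one with 0.014.

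**The alpha split is not an error.** A reader might infer that 0.01 + 0.04 is itself a mistake because it ignores the correlation between looks. The documents do not support that. The additive bound holds under any dependence, they promise only approximately 0.05, and 0.046 fits that. The bound also does not need the joint normality that 0.0440 relies on, which is a real consideration with 30 subjects in Stage 1 and site as a fixed effect across at least 17 sites.

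**sIGA.** A reader might carry the 0.0440 gain over to both primary endpoints. sIGA uses Fisher's exact test, which is discrete and conservative, so the bivariate normal figures do not describe it. No gain is shown there.

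**Phase 2 context.** SAP 2.11 reports no formal sample size assessment and disclaims multiplicity correction. That makes the last 0.004 of alpha unimportant. It does not excuse a final test whose true level is about one-ninth of its label (0.0044 against 0.04).

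**Conclusion.** The combination step is mis-scaled as written. Followed literally, it cuts the final test from 0.04 to about 0.0044, the overall error to about 0.014, and two-look power for a 7-point PASI difference at N = 75 from about 79% to about 54%. These figures assume two-sided tests, signed and approximately normal stage scores, stage information in the ratio 30:45, and the SAP's SD of 10. One-sided testing gives the same picture (overall 0.016).

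The error is conservative, so the written weights do not threaten a false positive claim. Inflation to about 0.08 arises only if the weights are corrected while the scores are left unsigned. The documents leave that open but do not call for it. The alpha split is sound once the formula is right, and changing 0.04 to 0.0440 is optional.

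**What to change.** In SAP 2.10 and in protocol 8.8 with its synopsis, before Stage 1 is unblinded:

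1. Write the combined statistic as Z = sqrt(0.4)\*Z1 + sqrt(0.6)\*Z2.
2. Define each stage Z as signed, either from a one-sided p-value in the direction of benefit or with the sign of the estimated effect attached.
3. State whether 0.01 and 0.04 are one- or two-sided.
4. Then choose the final level for PASI: keep 0.04 and record that it is deliberately conservative (overall 0.046), or set 0.0440 two-sided for about 1 point of power. Do not change the level before items 1 to 3 are settled.

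Dividing 0.4\*Z1 + 0.6\*Z2 by sqrt(0.52) would also restore unit variance (overall 0.0470), but 0.0440 would not then apply; the matching level is 0.0431.

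The cost is a formula and a few sentences in each document, with no operational change.

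### The Stage 1/Stage 2 combination applies weights 0.40 and 0.60 directly to the Z scores, so the combined score has null variance 0.52, which contradicts the stated final alpha of 0.04; sign and sidedness are also undefined

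*SAP*

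**What the plan says.** SAP 2.10 plans a Stage 1 analysis of the first 30 randomized subjects and a final analysis of both stages. The stated aim is "In order to ensure an overall alpha of approximately 0.05". The interim look is given a level of 0.01. For the end of the trial, the rule is that "the final analysis (Stage 1 and Stage 2 combined) will be analyzed at an alpha level of 0.04". A published method for modifying sample size in group sequential trials is cited as the means of preserving type I error.

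The weights are the planned sample fractions, 30/75 = 0.40 and 45/75 = 0.60. The mechanics are four steps. First, "The Stage 1 p-value will be converted to a Z score (standard normal score", and the same is done for Stage 2. Then "The Z scores will be combined using the weights previously indicated to create the combined Z score". As the last step, the plan says: "The combined Z score will be converted to a p-value".

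Protocol 8.8 and the Interim Analysis entry of the synopsis give the same steps. None of the three places mentions a square root, division by a standard deviation, the sidedness of the p-values, or the direction of effect.

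**The concern.** These steps produce the trial's primary p-values. A weighted sum of independent standard normal scores is itself standard normal only if the squared weights sum to 1. Here the weights sum to 1 and their squares do not. A programmer who follows the four steps would compare a score that is too narrow with standard normal limits and would lose power on PASI. Because PASI is tested first, a missed PASI result also removes the sIGA test.

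The second gap is separate. A two-sided p-value carries no direction, and the steps start from p-values. Unless the sign is restored, a Stage 1 result favouring placebo can add to a Stage 2 result favouring orticumab.

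**Working it through.** **Inputs.** Weights 0.40 and 0.60, final alpha 0.04 and Stage 1 alpha 0.01 (SAP 2.10). SD 10, PASI differences of 7 and 8 points, sIGA 40% against 10% (SAP 2.11). N = 75 at 2:1 (SAP 1.2), taken as 50:25 overall, 20:10 in Stage 1 and 30:15 in Stage 2. Sidedness is not stated; two-sided is assumed and one-sided is also shown.

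**The plan's own figures.**
- Alpha: 0.01 + 0.04 = 0.05, which matches the overall target as an upper bound.
- PASI power at two-sided 0.05: SE = 10·sqrt(1/50 + 1/25) = 2.449. For 7 points, 7/2.449 = 2.858 and Φ(2.858 − 1.960) = 0.815. For 8 points, 3.266 gives 0.904. These match the stated 80% and 90%.
- Final level of 0.04: with weights sqrt(0.40) and sqrt(0.60) the variance is 0.40 + 0.60 = 1 and the level is 0.0400. With the weights as written it is not reproduced, as follows.

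**Level as written, signed Z scores.**
- Var(0.40·Z1 + 0.60·Z2) = 0.16 + 0.36 = 0.52; SD = 0.721.
- Two-sided: the limit 2.054 becomes 2.054/0.721 = 2.848 on the true scale; level 2·(1 − Φ(2.848)) = 0.0044.
- One-sided 0.04: the true limit is 2.428; level 0.0076.
- Overall two-sided level including Stage 1 at 0.01 (numerical integration): 0.0137 as written, 0.0461 with square-root weights.

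**PASI power of the final test at two-sided 0.04** (normal approximation). With θ = difference/SE, the stage means are θ·sqrt(0.40) and θ·sqrt(0.60).
- Square-root weights: mean θ, SD 1.
- As written: mean θ·(0.40·sqrt(0.40) + 0.60·sqrt(0.60)) = 0.718·θ, SD 0.721. For 7 points the mean is 2.051 and power is Φ((2.051 − 2.054)/0.721) = 0.499.

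| N | Difference | Square-root weights | As written |
|---|---|---|---|
| 75 | 7 | 78.9% | 49.9% |
| 75 | 8 | 88.7% | 65.6% |
| 60 | 7 | 69.2% | 38.1% |
| 60 | 8 | 80.7% | 52.4% |

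The rows for 60 use the target number of completers, with SE 2.739.

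**If the sign is not kept.** Null rejection at nominal 0.04 depends on how two-sided stage p-values are turned into Z scores:

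| Conversion | As written | Square-root weights |
|---|---|---|
| Signed Z, two-sided | 0.0044 | 0.0400 |
| Absolute Z from p/2, converted back two-sided | 0.0086 | 0.0776 |
| Absolute Z from p/2, converted back one-sided | 0.029 | 0.152 |
| Inverse-normal(1 − p), converted back one-sided | 0.0076 | 0.0400 |

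No conversion with the written weights gives 0.04. With square-root weights and absolute Z converted back two-sided, opposite-direction stages account for 0.0388 of the 0.0776, about half. Example: Z1 = −2.5 and Z2 = +2.2. Absolute scores with square-root weights give 3.285 (p = 0.001); signed scores give 0.123 (p = 0.90).

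**sIGA, exact enumeration at 40% against 10%.** Take Zk = sign·inverse-normal(1 − p/2) from the two-sided Fisher p. Power at 0.04 is 68% with square-root weights and 33% with the written weights. One pooled Fisher test (50:25) has 77%.

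**The case against.** The best defence is that SAP 2.10 cites a type-I-preserving method and sets the final level at 0.04, and square-root weights give exactly that. The 0.40 and 0.60 may be sample fractions meant to enter through that method. This stands as a plausible account of intent. It does not rescue the text, because the numbered steps say otherwise and nothing elsewhere overrides them.

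Three stronger readings are tempting, and the documents do not support them.
- **That the trial will be tested at 0.0044.** This follows only from the literal weights with signed two-sided Z scores. The supportable statement is that the steps contradict the stated level.
- **That the plan uses unsigned p-values.** It is silent. SAP 2.15 adopts SAS defaults, which makes two-sided p-values likely, but it does not tell the analyst to discard the sign of the estimate. This is an omission.
- **That type I error is inflated, or that most of the power is lost.** The written weights are conservative under every conversion above. The 7.8% needs corrected weights together with absolute Z scores. The PASI loss at N = 75 is 23 to 29 percentage points.

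A further hazard belongs to one conversion only: under inverse-normal(1 − p), a Fisher p of 1 gives minus infinity. With absolute Z scores from p/2, p = 1 gives Z = 0.

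**Conclusion.** The concern holds as an internal contradiction plus an omission. The combination written in SAP 2.10, protocol 8.8 and the synopsis has null variance 0.52 and cannot give the stated 0.04. On the literal signed two-sided reading the level is 0.0044, and PASI power at N = 75 falls from 79% to 50% (7 points) or from 89% to 66% (8 points). The missing sign rule matters most once the weights are corrected, so both must be settled together.

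The level figures rest on independent, approximately normal stage scores. The power figures also rest on the SAP's SD of 10, exact 2:1 allocation within each stage, and no adjustment for site or baseline. This should be corrected before unblinding, because two competent programmers could otherwise produce different primary p-values, and a choice made afterwards could look driven by the result.

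**What to change.** Amend SAP 2.10, protocol 8.8 and the synopsis together.

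1. State combined Z = sqrt(0.40)·Z1 + sqrt(0.60)·Z2, with each Zk signed so that positive favours orticumab, tested at two-sided 0.04 (one-sided 0.02). The final-test level for PASI is then 0.0400.
2. For sIGA, define Zk = sign of the observed difference × inverse-normal(1 − p/2), with p the two-sided Fisher p-value, so that p = 1 gives Z = 0. One-sided Fisher p-values are less suitable here: power is 60% instead of 68%. The one-sided p still equals 1 whenever Stage 1 has no orticumab responder, which has probability 0.9^20 = 12% at a 10% response rate.

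**Alternative.** Run the final PASI and sIGA tests once on the pooled 75 subjects at 0.04. The 0.01 + 0.04 split still bounds alpha at 0.05, and sIGA power is 77%. This is valid only if the sponsor confirms that the sample size will not be changed after Stage 1. No rule for a change is given, but the plan calls the design adaptive and cites a sample-size-modification method.

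Either route costs wording only, with no added subjects or data. The pooled route gives up the freedom to change the sample size.
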